8.2.4.1 Impact of a reduced number of participants in the Incidence subcohort

These statistical power estimates are sensitive to key assumptions, including the number and age distribution of actual enrollment in the subcohort, selection of base incidence rates, how well the adjusted incidence rate reflects the success of risk enrichment of the cohort using eligibility risk factors, etc. Enrollment numbers that are less than original goals may be offset, to some degree, by conservative estimates used for base incidence rates, the effectiveness of risk enrichment strategies or the correlation between knee-specific incidence within individuals and the addition of incident knees from those with unilateral symptomatic knee OA at baseline. Table 8.5 gives an approximation of the effect that reduced numbers of incident symptomatic knee OA. All other things equal, a reduction in the size of the incidence cohort of 20% will result in a proportional drop in the number of incident cases from this cohort.

Table 8.5 Effect of reduced number of endpoints on power for detecting relative risks for	
incident symptomatic knee OA $^{\nu}$	

		For revised detectable effect ratios with a reduced sample size, raise the original effect ratio to power indicated						
		If detectable effect ratio based on original number of endpoints				ints		
If number of cases drops by	Detectable risk ratio is raised to power	1.3	1.4	1.5	1.6	1.7	1.8	1.9
		Then the detectable effect ratio with reduced sample size is:						
10%	1.05	1.32	1.42	1.53	1.64	1.75	1.85	1.96
20%	1.11	1.34	1.45	1.57	1.68	1.80	1.92	2.04
30%	1.18	1.36	1.49	1.61	1.74	1.87	2.00	2.13

8.2.5 Power for Analyses of Progression Biomarkers

Rates of change in key measures of progression such as WOMAC and especially rates of joint space loss could be speculated, but since it is not known whether the rates of change in OAI subjects will more closely resemble those in a community sample with a mixture of symptomatic and radiographic OA(143) or the higher rates observed in clinical samples,(144, 145) projecting such rates would be speculative. A community sample with symptomatic knee OA will probably be somewhere in between. Moreover, power analysis for progression biomarkers will focus not on detecting loss of joint space or decline in WOMAC scores, but rather on testing correlations between changes in these

^v These calculations utilize the fact when the effects are ratios, and from a statistical point of view handled on the log scale, then the loss in detectable effect size for a change in the effective sample size can be estimated by raising the effect size to a power calculated based on the fact that the detectable effect size is proportional to the square root of the effective sample size.

and other variables. Therefore, power for these analyses are not substantially dependent on the rates of change.

An analysis of predictors of progression of knee OA (called OA progression below) might test the effect of risk factors (dichotomous predictors) on outcome (e.g. change in disability and joint space) in knees with prevalent OA at baseline over the follow-up period using random effects models. Based on the original study goals, there will be an expected 480 subjects with bilateral prevalent knee OA and 320 subjects with prevalent unilateral OA. Allowing for withdrawal from the study and the correlation between knees in the same person, the equivalent of about 620 independent knees with symptomatic OA at baseline will have four years of follow-up and these are used to determine the power for OA progression.

The WOMAC disability scale and WOMAC pain scale are potential outcomes in this analysis. For the WOMAC disability scale (Likert version, range 0-68) a standard deviation of 16.29 is expected for a single administration(146) with an expected correlation of 0.70 between yearly WOMAC assessments for a subject. Using the 5 assessments, it is possible to obtain yearly change with a standard deviation of 2.82 units. The WOMAC pain scale (Likert version, range 0-20) has a standard deviation of 4.32 units for a single measure. Using 5 measures per subject, a standard deviation of 0.75 will hold for yearly change in WOMAC pain scale.

•	n WOMAC scores de alence in knees with	
Exposure	Detectable	Detectable
Prevalence	WOMAC	WOMAC Pain
(%)	Disability Yearly	Yearly Change
	Change Difference	Difference
50	0.636	0.169
33	0.676	0.180
25	0.734	0.195
10	1.059	0.282

Table 8.6 gives the differences in yearly change in the two WOMAC scores that can be detected with 80% power using two-sided 0.05 significance tests for predictors of varying prevalence. For example, a difference of 0.676 units in yearly WOMAC disability change, which would account for a 2.7 unit difference at the end of 4 years of follow-up, could be detected for a risk factor affecting one third of subjects.

Candidate biomarkers for OA progression can be evaluated through the correlation of their time trend (slope over time in the random effects model) with the time trend of the WOMAC disability and pain scales. These correlations are attenuated by measurement error in both the WOMAC scales and in the biomarker. While there will be many candidate biomarkers, Table 8.7 shows results using cartilage volume as an example.

WOMAC	True	Attenuated	95% CI for Attenuated
Scale	Correlatio	Correlation	Correlation
	n		
Pain	0.20	0.169	(0.091, 0.244)
Pain	0.40	0.338	(0.266, 0.406)
Pain	0.60	0.507	(0.446, 0.563)
Pain	0.80	0.676	(0.631, 0.717)
Pain	0.90	0.761	(0.725, 0.792)
Disability	0.20	0.176	(0.098, 0.251)
Disability	0.40	0.351	(0.280, 0.419)
Disability	0.60	0.527	(0.468, 0.582)
Disability	0.80	0.703	(0.661, 0.741)
Disability	0.90	0.791	(0.759, 0.819)

Published test-retest reliabilities (ICC values) for the WOMAC pain scale are 0.65, 0.74, and 0.90, and values of 0.71, 0.80 and 0.92 for the disability scale. For calculating the attenuated correlation between cartilage volume change and WOMAC change, the moderate ICC values of 0.74 and 0.80 for pain and disability,(43) respectively, as well as the ICC for cartilage volume were used. Table 8.3 shows various true correlation values, the corresponding attenuated correlation, and the 95% confidence interval for the attenuated correlation. For example, if the true correlation between the time trend in WOMAC pain and the time trend in cartilage volume were 0.6, we would expect an attenuated correlation of 0.507 with a 95% confidence interval extending from 0.446 to 0.563. This should allow good discrimination between candidate biomarkers for progression with reasonable levels of correlation with WOMAC scales.

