Exposure	Relative Risk
Prevalence	detectable with
(%)	80% power
50	1.56
33	1.57
25	1.62
10	1.91

nested case-control analysis using an MRIderived risk factor or a biochemical marker as a predictor of time to incident OA. For this it is conservatively assumed that image or biochemical marker data would be available from about 300 case knees and 1200 control knees. Because the number of cases and controls is reduced in the case-control analysis, the detectable relative risks are larger. Even for exposures with 10% prevalence, there is 80% power to detect a relative risk of 1.62 in all subjects, and 1.91 in the case-control analyses.

Analysis of the association of biomarkers with incident OA to evaluate surrogacy, in the case-cohort sample with full biomarker data, might consider the correlation between the time trend in the biomarker with time trend in log odds of incident OA from a logistic regression model having a random slope (fit using the SAS NLMIXED procedure). These trends are estimated with some error, due to instrument-specific measurement error, making the observed correlation values have some bias toward 0. The accuracy calculations below take this attenuation toward 0 into account.

To select the most promising biomarkers, 95% confidence intervals could be used, and Table 8.4 displays results for the attenuated correlation values. Confidence intervals for the correlations are found using Fisher's Z-

transformation.(141) The table uses the MRI cartilage volume, which has an interclass correlation of 0.92 at the medial tibia,(142) as an example biomarker. Table 8.4 shows various correlation values between time trends in the first column, the attenuated correlation (allowing for measurement error) in the second column,

time trend for	Table 8.4 Precision of attenuated correlations betweenime trend for cartilage volume change and the time trendin log odds of incident symptomatic OA				
True	Attenuated	95% CI for Attenuated			
Correlation	Correlation	Correlation			
0.20	0.196	(0.136, 0.254)			
0.40	0.393	(0.340, 0.444)			
0.60	0.589	(0.548, 0.628)			
0.80	0.786	(0.761, 0.808)			
0.90	0.884	(0.870, 0.897)			

and the 95% confidence interval (CI) for the attenuated correlation in the third column. These results show that correlations with incident OA will be estimated with good precision, having confidence interval widths close to 0.1 for moderate correlation values.

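### Tables 8.6 and 8.7 rest on incompatible assumptions about WOMAC slopes, so the stated power and the stated precision cannot both hold

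*Protocol*

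**What the plan says.** Section 8.2.5 builds its WOMAC power on three inputs for disability: "a standard deviation of 16.29 is expected for a single administration", taken "with an expected correlation of 0.70 between yearly WOMAC assessments for a subject", and five assessments. The result is "Using the 5 assessments, it is possible to obtain yearly change with a standard deviation of 2.82 units". For pain, the scale "has a standard deviation of 4.32 units for a single measure", and "Using 5 measures per subject, a standard deviation of 0.75 will hold for yearly change in WOMAC pain scale". These SDs feed Table 8.6, which gives differences in yearly change detectable with 80% power (two-sided 0.05) in about 620 effective independent knees. At 50% exposure prevalence they are 0.636 for disability and 0.169 for pain.

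Table 8.7 then gives the precision of the correlation between the WOMAC slope and the cartilage-volume slope from a random effects model. It attenuates that correlation for measurement error using "the moderate ICC values of 0.74 and 0.80 for pain and disability", which the text identifies as published test-retest reliabilities, together with the ICC for cartilage volume. Section 8.2.4 introduces the latter as "MRI cartilage volume, which has an interclass correlation of 0.92 at the medial tibia". The protocol concludes that candidate markers can be told apart well.

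The same section declines to project rates of progression, on the ground that "power for these analyses are not substantially dependent on the rates of change".

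**The concern.** The two tables describe the same WOMAC slopes in the same knees over the same four years, so they need the same variance components. A constant between-visit correlation is a random-intercept structure: slopes differ between knees only through residual scatter, and their reliability is zero. Table 8.7 needs the opposite, since a correlation between true slopes exists only if true slopes vary. A test-retest ICC does not supply that variation. It says how reproducible one score is, not how much of a four-year slope is real.

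At stake is what Section 8 tells users of the resource. Evaluating biomarkers is the second principal objective, Section 8.2.3 says the design gives adequate precision for biomarker-endpoint relationships, and Section 4.5.1 refers to Section 8 for the adequacy of the sample. Outside investigators will plan analyses from these tables.

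**Working it through.** **Inputs (all from Section 8.2.5 unless noted).** Single-visit SD 16.29 (disability) and 4.32 (pain); between-visit correlation 0.70, stated for disability and also reproducing the pain figure; five annual assessments at t = 0 to 4, so the sum of squares of time is 10; 620 effective knees; WOMAC ICCs 0.80 and 0.74; cartilage ICC 0.92 as stated in Section 8.2.4.

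**1. Reproducing the protocol's figures.**
- Slope SD under constant correlation = SD × sqrt((1 − 0.70)/10). Disability: 16.29 × sqrt(0.03) = 2.82. Pain: 4.32 × sqrt(0.03) = 0.748, stated as 0.75.
- Table 8.6: detectable difference = 2.80 × slope SD / sqrt(620 × p × (1 − p)). For disability at p = 50, 33, 25 and 10% this gives 0.635, 0.675, 0.733 and 1.058; printed 0.636, 0.676, 0.734 and 1.059. Pain reproduces equally closely.
- Table 8.7: attenuated r = true r × sqrt(WOMAC ICC × cartilage ICC), with a Fisher-z interval. With 0.74 or 0.80, a cartilage ICC of 0.965 and n = 620, a true 0.6 gives 0.507 (0.446, 0.563) for pain and 0.527 (0.468, 0.582) for disability, as printed.

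Each table is therefore arithmetically sound on its own inputs. The inputs conflict.

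**2. Keep Table 8.7's reliabilities.** If R is the share of observed slope variance that is true, total slope SD = error SD of the slope / sqrt(1 − R). Two readings of the error SD bracket the answer:
- Error from the ICC: 16.29 × sqrt(0.20/10) = 2.30 and 4.32 × sqrt(0.26/10) = 0.697. Totals: 2.30/sqrt(0.20) = 5.15 and 0.697/sqrt(0.26) = 1.37.
- All of 2.82 and 0.748 taken as error. Totals: 2.82/sqrt(0.20) = 6.31 and 0.748/sqrt(0.26) = 1.47.

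| | Stated slope SD | Total slope SD | Stated difference, p = 50% | Recomputed difference | Power at stated difference |
|---|---|---|---|---|---|
| Disability | 2.82 | 5.15-6.31 | 0.636 | 1.16-1.42 | 34-24% |
| Pain | 0.75 | 1.37-1.47 | 0.169 | 0.31-0.33 | 34-30% |

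**3. Keep 2.82 and 0.75 as total slope SDs.** Read strictly, constant correlation gives slope reliability 0. The most generous reading credits all within-person variance beyond test-retest error to true slope: R = 1 − (1 − ICC)/(1 − 0.70).
- Disability: 1 − 0.20/0.30 = 0.33. Pain: 1 − 0.26/0.30 = 0.13.
- A true 0.6, with cartilage reliability left at 0.965, appears as 0.6 × sqrt(0.333 × 0.965) = 0.34 (0.27, 0.41) for disability and 0.6 × sqrt(0.133 × 0.965) = 0.215 (0.14, 0.29) for pain.

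**4. Could both tables hold?** Reliabilities of 0.80 and 0.74 at the stated total SDs need single-visit ICCs of 1 − 0.20 × 0.30 = 0.94 and 1 − 0.26 × 0.30 = 0.92. The highest published values the protocol quotes are 0.92 and 0.90, which give slope reliabilities of at most 0.73 and 0.67.

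**5. A middle case (assumption, for illustration).** An autoregressive true score plus test-retest error, with adjacent-year correlation 0.70, gives slope reliabilities 0.68 and 0.43 and slope SDs 4.10 and 0.92. Detectable differences become about 0.92 and 0.21, and a true 0.6 appears as about 0.49 and 0.38. Both tables move.

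**6. Cartilage ICC.** Back-solving the printed rows gives (0.884/0.9)² = 0.965 in Table 8.4, and (0.169/0.2)²/0.74 = 0.965 and (0.791/0.9)²/0.80 = 0.966 in Table 8.7. The text says 0.92. With 0.92, 0.507 becomes 0.495 and 0.527 becomes 0.515.

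**The case against.** **The covariance structure is inferred.** True: the protocol prints one correlation and no formula. But the match is exact for both scales, and step 3 does not depend on the inference, since it grants all variance beyond test-retest error to true slope.

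**The enlarged differences are not a corrected Table 8.6.** This stands. A reader might take 1.42/0.636, a factor of about 2.2, as the size of the error. That figure assumes the very reliability in dispute. It implies a true-slope SD of about 5.6 per year. With slopes independent of baseline, the year-4 SD would be sqrt(16.29² + 16 × 5.64²), about 28 on a 0-68 scale, and the baseline-to-year-4 correlation about 0.41. Neither fits 16.29 and 0.70. The range shows what keeping Table 8.7 would cost, no more.

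**Loss of discrimination is not established.** A reader might infer from overlapping intervals that markers with true correlations of 0.4 and 0.6 cannot be separated. Overlap is not a test, and Section 8.2.3 names a parametric bootstrap for comparing correlations. Treating the two as independent with n = 620, the difference has z of about 2.2 at disability reliability 0.33 and about 1.3 at pain reliability 0.13. On the printed values z exceeds 3.5 for both. Discrimination is weaker and, for pain, doubtful.

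**The sentence on rates of change is about mean rates.** Also right. A reader might call it wrong and strike it, but a slope difference or a slope correlation does not depend on the mean slope. It is incomplete because it omits the spread of the rates.

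**Enrolment and status.** Section 4.5.1 reports 1,330 Progression participants against 800 planned. Scaling 620 by 1,330/800 gives about 1,030 knees and shrinks differences and interval widths by about 22%. Disability is then still 0.90-1.10, against the printed 0.636. The analyses are offered as examples and no decision rule rests on them, which limits the consequence but not the inconsistency.

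**Conclusion.** The concern holds in this form: the 80% power in Table 8.6 and the precision in Table 8.7 require different variances for the same WOMAC slopes. Using the ICCs the protocol chose, either the detectable differences roughly double (1.16-1.42 and 0.31-0.33) or slope reliability is at most 0.33 and 0.13 and a true 0.6 appears as at most about 0.34 and 0.215. These sizes assume 620 effective knees, five complete annual assessments and, for the correlations, the cartilage reliability of 0.965 that the tables use.

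The documents do not show which table is wrong, only that at least one is materially optimistic. They do not support the view that markers are inseparable, that the statement about rates of change is false, or that any single factor corrects Table 8.6. The cartilage ICC mismatch is real but minor.

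**What to change.** - State one range for the between-knee SD of true WOMAC slopes and carry it through both tables: total slope SD for Table 8.6, and slope reliability (true-slope variance over total) for Table 8.7. Apply the same logic to the cartilage slope.
- Restate the detectable differences and attenuated correlations over that range, and qualify the claim that candidate markers can be told apart well, especially for pain.
- Keep the sentence on rates of change as it applies to mean rates, and add that power and precision depend on the between-knee variance of the rates.
- Use one cartilage ICC in the text and in Tables 8.4 and 8.7.
- Update the slope variance from the first follow-up data release, and restate the tables for the enrolled 1,330.

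The cost is statistician time and revised tables. Enrolment and data collection are untouched. The stated precision will look less favourable, partly offset by the larger Progression subcohort.

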9.0 STUDY ORGANIZATION

9.1 Overview

The Study organization of OAI will include 4 clinical centers, the data coordinating center and its subcontractors (including the imaging quality assurance center, core laboratory and scientific advisory and analysis center), the Project Office at the National Institute of Arthritis and Musculoskeletal and Skin Diseases (NIAMS), and several standing and ad hoc study committees. The OAI committees will draw their members from the investigators and staff of the participating centers, from the NIH and the

V 1.1 6.21.06

pharmaceutical partners of OAI. An external Observational Study Monitoring Board (OSMB) and an external Biospecimen Resource Allocation Committee (BRAC) will report directly to the NIAMS

9.2 Federal Sponsors

The National Institute of Arthritis and Musculoskeletal and Skin Diseases (NIAMS - http://www.niams.nih.gov/) and the National Institute on Aging (NIA - http://www.nia.nih.gov/) will lead the OAI at the National Institutes of Health (NIH - http://www.nih.gov/). Other public partners in the Osteoarthritis Initiative at the NIH will include the Office of Research on Women's Health, National Institute of Dental and Craniofacial Research, National Center on Minority Health and Health Disparities, National Institute Of Biomedical Imaging and Bioengineering, and the National Center for Complementary and Alternative Medicine. The National Center for Research Resources, the Office of Technology Transfer, the Office of the General Counsel, and the Office of Science Policy have also played pivotal roles in the establishment of this initiative. Another Department of Health and Human Services component the will be involved is the Center for Drug Evaluation and Research of the Food and Drug Administration.

NIAMS is the lead institute of the consortium of NIH institutes, centers and offices sponsoring the study. The study will be administered through contracts from NIAMS. The contracts office and the project office at NIAMS are responsible for the overall administration and fiscal management of the study. Representatives from this office will participate in all phases of the study and be active on OAI committees. The NIAMS project office will organize the OSMB and the BRAC and coordinate their activities. NIAMS reserves the right to terminate the study in the event of unforeseen circumstances.

Funds from NIH institutes and centers and a group of pharmaceutical company sponsors will be combined with a 7-year commitment to fund the OAI.

9.3 Industry Sponsors

A group of pharmaceutical companies will co-fund the OAI. Private-sector funding for the OAI will be managed by the Foundation for the National Institutes of Health (http://www.fnih.org/). Representatives of the sponsoring companies will participate in all phases of the study and be active on OAI committees. The sponsors are Novartis Pharmaceuticals, Merck and Co, Inc, Pfizer, Inc. and GlaxoSmithKline.

9.4 Clinical Centers

Each clinical center will consist of an interdisciplinary team of clinical investigators who provide the areas of expertise necessary for the successful completion of the OAI protocol. Clinical center responsibilities will include:

- collaborate in the design and monitoring of the study, including regular attendance at Steering Committee meetings;
- recruit participants for the study according to inclusion and exclusion criteria and in numbers and strata specified in the protocol;

- purchase, install and operate a Siemens Trio 3.0 Tesla MR scanner and acquire scans according to study protocols;
- arrange for bone and joint radiography to be performed according to study protocols;
- perform all study procedures according protocol and collect and manage data in a standardized fashion;
- make provisions to ensure the safety, confidentiality and ethical treatment of study participants;
- collaborate in the analysis and dissemination of study results.

9.5 Data Coordinating Center

The OAI coordinating center at UCSF, under the direction of [name], will have operational responsibility for the design, implementation, coordination and monitoring of all aspects of the study. Specific responsibilities of the coordinating center will include:

- develop the study protocol under the guidance of the steering committee;
- prepare the data collection forms, manuals, recruitment and other study materials;
- develop and implement the study data management and communication systems;
- perform central training of study personnel and monitor clinic performance;
- perform data management and quality assurance of study data;
- prepare data files and documentation for use by OAI investigators and the larger community of scientists;
- develop and maintain the study and public web sites for OAI;
- distribute data files, documentation and images to users;
- coordinate the activities of subcontractors, reading centers and core labs;
- monitor study progress and report on progress to the steering committee and OSMB;
- arrange and coordinate study teleconferences and meetings;
- provide biostatistical expertise to OAI investigators and other users of OAI data;
- hold public meetings for data and image users to provide information on use of the dataset;
- prepare, in collaboration with the clinical center and other OAI investigators, manuscripts of the study results.

The central imaging Quality Assurance Center will be Synarc, Inc, of San Francisco, Ca., under the direction of [name]. The imaging QA center will be the scientific and operational hub for imaging related activities within the OAI. Synarc, Inc, will function as a subcontractor to the coordinating center. The Biospecimen repository for the study will be located at Fisher Bioservices, Inc, in Rockville, MD, under a subcontract to the coordinating center. The Boston University Multidisciplinary Clinical Research Center, under the direction of [name], will provide expertise to the OAI in methodological, analytical and biostatistical areas of direct relevance to osteoarthritis. Boston University is a subcontractor to the coordinating center.

